5.6.4.5 Inpatient Hospitalizations due to Epilepsy

The number of inpatient epilepsy-related hospitalizations since the previous visit are recorded at every visit starting from Visit 2.

The number of patients with inpatient epilepsy-related hospitalizations will be presented by visit, including OLE visits.

5.6.4.6 Growth and Development

IGF-1 levels will be analyzed as part of the clinical laboratory testing. IGF-1 levels will be summarized on a continuous scale, including change from baseline, by treatment arm.

For the blinded phase only, change from baseline to the end of treatment visit for IGF-1 levels will also be plotted against the Tanner Stages, weight, and height recorded at baseline.

The pubic hair growth (both sexes), genital (males only) and breast (females only) development of all adolescent patients (i.e., 10 to less than 18 years of age at the time of signing the informed consent form, or earlier if clinically indicated by onset of menarche or other signs of precocious puberty) will be assessed using Tanner Staging. The patients will undergo a discreet physical examination and be assigned a value under each category of Pubic Hair Growth (both sexes), Genitals (male patients only), and Breasts (female patients only).

Tanner Stages will be summarized on a categorical scale, by treatment arm.

5.6.4.7 Menstruation

Menstruation details will be summarized as appropriate, including any changes in normal cycles, by treatment arm.

5.7 Other Measures

5.7.1 Concomitant Medication

Medications will be coded using the World Health Organization Drug Dictionary, Version September 2016.

A medication will be considered concomitant for each phase if it has a start date on or after the first dose of IMP for the corresponding phase or if it was started prior to the first dose of IMP and was ongoing. If a medication has a partial or missing start/stop date and it is unclear from the date whether the medication was taken after the first dose of IMP then it will be considered concomitant.

For summaries and listings of medications the following approach will be used to determine the Anatomical Therapeutic Chemical (ATC) term to be presented:

- If coded to level 4 then the level 4 coded term will be presented.
- If coding is not performed at level 4 but level 3 coding is present, then level 3 coded term will be presented.
- If coding is not performed at level 3 but level 2 coding is present, then the level 2 coded term will be presented.
- If coding is not performed at level 2 but level 1 coding is present, then the level 1 coded term will be presented.

Summaries of each of the following by ATC term and preferred term will be summarized by absolute counts (n) and percentages (%), separately for the blinded and OLE phase (unless stated otherwise):

- History of AEDs (blinded phase only);
- Concomitant AEDs;
- Concomitant rescue medications; and
- Other concomitant medications.

The ATC term, preferred term, reported generic name and reported brand name will be listed.

An additional summary table will be produced for concomitant antiepileptic therapies, displaying the number and percentage of patients with a vagus nerve stimulation device or on a ketogenic diet.

The start day and stop day will be included in the listing according to Section 5.1.2. If the date is partial and the exact day is unknown then the text 'pre' or 'post' will replace the start or stop day if it is clear from the partial date that the medication started or stopped prior to or after the first dose of IMP.

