5.4.3 Demographic Data and Baseline Characteristics

The following demographic data will be summarized by treatment arm and overall for the safety, ITT, PP and OLE safety analysis sets:

- Age (years);
- Age group (1–6 years, 7–11 years, 12–17 years and 18–65 years);
- Sex;
- Race;
- Country;
- Region (US, Rest of the World);
- Weight at baseline (kg);
- Height at baseline (cm);
- Body mass index at baseline (kg/m²).

Age will be calculated as:

$$(\text{Date of screening} - \text{date of birth}) \div 365.25.$$

The following baseline characteristics will be summarized by treatment arm and overall for the safety, ITT, PP and OLE safety analysis sets:

- Average number of TSC-associated seizures per 28 days during baseline.
- Average number of total seizures per 28 days during baseline.
- Number of patients with seizures during the baseline period, by seizure type.
- Number of AEDs a patient has used, prior to the trial and is no longer taking.

- Number of AEDs a patient is currently taking.
- Total number of prior and current AEDs.
- Number of patients taking clobazam (Yes, No, and if no, Prior).
- Number of patients taking valproic acid (Yes, No, and if no, Prior).
- Number of patients taking levetiracetam (Yes, No, and if no, Prior).
- Number of patients taking vigabatrin (Yes, No, and if no, Prior).

The number of prior AEDs no longer taking will be taken from the 'History of antiepileptic medications and therapies' CRF page. The number of AEDs a patient is currently taking is based on the 'Concomitant antiepileptic medications' CRF page. If a patient has a medication listed on both the 'History of antiepileptic medications and therapies' and 'Concomitant antiepileptic medications' CRF pages and the medication is considered concomitant (see Section 5.7.1) for the double-blind phase, then this will not be included in the number of prior AEDs no longer taking. AEDs starting after the last dose of IMP during the double-blind phase will not be counted.

Patients taking the same AED type, but where the AED were coded to different generic terms will be counted only once within the AED type. For example, valproate sodium, valproic acid, valproate semisodium and ergenyl chrono will all be counted as valproic acid and counted once under that term.

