The number of patients taking clobazam is defined as the number of patients taking clobazam at any point during baseline period or treatment period. The same definition will apply for the number of patients taking each of the other AEDs. The number of patients taking other AED types will also be presented if the overall frequency of patients taking the AED is >25%.

Previous cannabis use will be included within the baseline characteristics listing.

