5.6.2 Adverse Events

All reported AEs will be classified by system organ class (SOC), preferred term and lower level term using Version 19.1 of MedDRA.

Summaries will be presented by treatment arm as well as SOC and preferred term.

A blinded phase treatment emergent AE (TEAE) is defined as an AE with a start date on or after the first dose of IMP during the blinded phase up to and including the date of first dose of the OLE phase (OLE Day 1). An OLE phase TEAE is defined as an AE with a start date on or after the OLE Day 1. If an AE has a partial start date and it is unclear from the partial date (or the stop date) whether the AE started prior to or post first dose of IMP then the AE will be considered treatment emergent and if it is unclear which phase the event started, it will be assigned to both phases. If the start date of the AE is the same as the date of first dose of IMP from the blinded phase and the plausible relationship to IMP is marked on the CRF as "Prior to study medication" then the AE will not be considered treatment emergent.

An AE will be considered treatment-related if the plausibility relationship to trial medication is recorded on the CRF as 'yes'. If the data on plausibility relationship to trial medication is missing then the AE will be considered treatment-related.

An AE will be considered leading to permanent discontinuation of IMP if the action taken with IMP is recorded on the CRF as 'study medication stopped' or the outcome is recorded on the CRF as 'patient died'.

An AE will be considered leading to IMP dose reduction excluding permanent discontinuation if the action taken with IMP is recorded on the CRF as 'dose reduced', 'dose reduced temporarily' or 'study medication interrupted'.

An AE will be considered leading to temporary IMP dose reduction if the action taken with IMP is recorded on the CRF as 'dose reduced temporarily'.

An AE will be considered leading to permanent IMP dose reduction excluding permanent discontinuation if the action taken with IMP is recorded on the CRF as 'dose reduced'.

An AE will be considered fatal if the outcome is recorded on the CRF as 'patient died'.

The following summaries will be generated separately for the blinded and OLE phase (counts are by patient unless specified otherwise):

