2.3.3 Robustness to Withdrawn Patients

There were higher proportions of patients in each treatment arm that withdrew during the blinded phase treatment period when compared with placebo. In order to assess the robustness of the results, 2 analyses in the following sections are proposed.

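### SAP 5.7.1 gives blinded-phase concomitant medication no end date, so drugs first started in the OLE fall into the descriptive blinded-phase Tables 6.3 to 6.5 and can disturb the prior-AED count

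*SAP*

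**What the plan says.** Section 5.7.1 defines concomitant status phase by phase. A medication qualifies "if it has a start date on or after the first dose of IMP for the corresponding phase". A second limb covers drugs already in use at that date: "or if it was started prior to the first dose of IMP and was ongoing". Where dates are partial and the timing is unclear, it is treated as concomitant. The summaries of concomitant AEDs, rescue medications and other medications are then produced "separately for the blinded and OLE phase (unless stated otherwise"). In Appendix 6 the blinded-phase versions are Tables 6.3, 6.4 and 6.5, on the safety analysis set.

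Section 5.4.3 uses this definition to count prior AEDs. An AED on both the history page and the concomitant page of the CRF is left out of the prior count when "the medication is considered concomitant (see Section 5.7.1) for the double-blind phase". The same paragraph ends: "AEDs starting after the last dose of IMP during the double-blind phase will not be counted".

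Section 5.5.5 uses the resulting counts as effect modifiers for the primary endpoint and the 50% responder endpoint: prior AEDs (<5, ≥5) and prior plus concurrent AEDs (<8, ≥8).

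**The concern.** The only phase-specific date in 5.7.1 is a lower bound. A drug first taken in the eighth month of the OLE starts after the first blinded dose as well as after the first OLE dose, so it satisfies the definition for both phases.

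Readers use the blinded-phase medication tables to judge whether background and rescue treatment were alike in the arms while the blinded comparison ran. If OLE starts are mixed in, the tables no longer describe that period. They would also change at each later data cut, although the blinded phase had finished.

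The second consequence is through 5.4.3. A baseline characteristic, the number of AEDs tried before the trial, can be altered by a prescription written after the last blinded dose.

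**Working it through.** **1. The rule beside the SAP's other rules on the same period**

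| Item | Section | End of the blinded window |
|---|---|---|
| Concomitant medication | 5.7.1 | none stated |
| Treatment-emergent AEs | 5.6.2 | "up to and including the date of first dose of the OLE phase (OLE Day 1") |
| AED counts | 5.4.3 | AEDs starting after the last double-blind dose not counted |
| Use of a named AED, e.g. clobazam | 5.4.3 | "taking clobazam at any point during baseline period or treatment period" |
| Days of rescue medication | 5.5.4.3 | Visit 3 to Visit 10 |

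Section 5.7.1 is the exception. The interim-reporting rule in 5.1.4.1 does not fill the gap: it selects records by the calendar date of the data cut, not by phase, so an OLE start before the cut stays in.

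**2. What the gap reaches**

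- Tables 6.3 to 6.5 are reached directly. They are counts and percentages with no test.
- The rescue-medication ANCOVA is not reached. It uses days of use collected at visits within its own window.
- The subgroups by named AED are not reached. Their window is the baseline or treatment period.
- The prior-AED count, and the total built on it, are reached through the cross-reference in 5.4.3.

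**3. The 5.4.3 route, step by step**

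Take a patient with five AEDs on the history page, all stopped before the trial, one of which is restarted in the OLE and so also appears on the concomitant page.

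- The restart falls after the first blinded dose, so under 5.7.1 the drug is concomitant for the double-blind phase.
- It is therefore left out of the prior count: 5 − 1 = 4. The patient moves from the ≥5 group to the <5 group.
- It started after the last blinded dose, so it is not counted as current either.
- The prior-plus-concurrent total is also one too low. A total of 8 becomes 7, which crosses the <8/≥8 boundary.

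**4. Length of the window**

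Inputs: the treatment period is Day 1 to Day 113 (5.1.3.4); OLE Day 1 is expected to be the end-of-treatment visit (5.1.2), taken as Day 113; the OLE lasts at most 1 year (3.1), taken as 365 days.

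- Literal blinded-phase window for a full-year OLE: 113 + 365 − 1 = 477 days.
- Ratio to the blinded phase: 477/113 = 4.2.
- Share outside the blinded phase: (477 − 113)/477 = 364/477 = 76%.

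This is a share of calendar time, not of patients or records.

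**5. Possible effect on a table row (all rates assumed; the SAP gives none)**

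Let p be the share of an arm starting a drug in the blinded phase, r the OLE start rate per 113 days, and c the share entering the OLE for a full year. With nobody on the drug at Day 1:

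tabulated share = 1 − (1 − p) × [1 − c + c × (1 − r)^(364/113)]

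Take p = 10% on placebo and 5% on active, a true ratio (active/placebo) of 0.50.

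- r = 5%, c = 50%: 16.9% vs 12.2%, ratio 0.73.
- r = 10%, c = 100%: 35.9% vs 32.3%, ratio 0.90.

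The definition also counts drugs already being taken at Day 1, and a patient enters a row once. Suppose half of each arm already takes the drug, and the shares above apply to the other half.

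- True ratio: (0.5 + 0.5 × 0.05)/(0.5 + 0.5 × 0.10) = 0.525/0.550 = 0.95.
- Tabulated, first case: (0.5 + 0.5 × 0.122)/(0.5 + 0.5 × 0.169) = 0.561/0.585 = 0.96.
- Tabulated, second case: (0.5 + 0.5 × 0.323)/(0.5 + 0.5 × 0.359) = 0.662/0.680 = 0.97.

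Under these assumptions the distortion can be clear for a drug that few patients take at Day 1, and close to nothing for one that many already take.

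**The case against.** The strongest reply is that separation of the phases is plainly intended. Section 5.7.1 speaks of each phase and reports them separately, and the phase start dates and the blinded treatment period are fixed elsewhere. A programmer may well apply the intended limit, and start and stop days are in the listings, so a reader can check. This makes a wrong table less likely. It does not supply the missing condition, and the SAP states that condition for AEs and AED counts.

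A reader might infer that the tested comparison of rescue use is biased. The documents do not support this, because that analysis has its own window and data source.

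A reader might also infer that replacement AEDs begun after withdrawal load onto the active arms, since the SAP addendum, 2.3.3, reports: "There were higher proportions of patients in each treatment arm that withdrew during the blinded phase treatment period when compared with placebo". That sentence concerns withdrawal only and says nothing of later AEDs. The AE rule in 5.6.2 likewise gives no end date for patients who never enter the OLE, so counting medications after IMP stops is not out of line with it. No direction of bias from withdrawals is established.

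On 5.4.3, the closing sentence of the paragraph can be read as disregarding a late restart altogether, which would leave the prior entry in place. That reading is fair but not the only one, and the cross-reference to 5.7.1 points the other way. The case also needs an unusual history: an AED stopped before the trial and restarted only after the last blinded dose.

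**Conclusion.** The point stands as an error in a definition with limited reach. Followed as written, 5.7.1 puts medications first started in the OLE into the blinded-phase Tables 6.3 to 6.5, and 5.4.3 can lose a restarted AED from both the prior and the current count. The first affects descriptive tables by arm. The second affects a baseline characteristic and two exploratory subgroup splits, probably in few patients.

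No primary, key secondary or rescue-medication test changes. The size cannot be given: the SAP has no start rates, no OLE entry rate and no share already on each drug. The 76% rests on a full-year OLE beginning on Day 113, and the ratios above are illustrations under assumed rates.

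**What to change.** In 5.7.1, define a medication as concomitant for the blinded phase if it was taken on or after the first blinded dose and was started before the first OLE dose (OLE Day 1). State an end date for patients who do not enter the OLE, for example the last blinded dose or the end of taper or follow-up, and use it consistently.

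In 5.4.3, remove an AED from the prior count only if it was taken between the first and last blinded dose. An AED restarted later then stays a prior AED and is not counted as current.

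The cost is a short wording change in two sections and one extra date condition in the program. Blinded-phase medication counts become smaller, by an amount that depends on how many drugs were first started later.

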5.7.2 Pharmacokinetics of CBD and its Major Metabolites

Samples for PK analysis are taken on Visit 3 (first dose, Day 1) and Visit 10 (last maintenance dose of the blinded phase, Day 113) for patients weighing more than 20 kg. For patients recruited under Protocol Version 2, PK samples were taken at the following time-points:

- Prior to administration of IMP, ≤ 0.0 hours pre-dose on Visit 3 or C_{trough} at steady state (Visit 10).
- ≥ 4.0 hours to ≤ 5.0 hours.
- ≥ 6.0 hours to ≤ 7.0 hours.
- ≥ 8.0 hours to ≤ 10.0 hours, for patients 18 years or older.

Patients recruited under Protocol Version 3 onwards, PK samples were taken at the following time-points:

- Prior to administration of IMP, ≤ 0.0 hours pre-dose on Visit 3 or C_{trough} at steady state (Visit 10).
- ≥ 2.0 hours to ≤ 3.0 hours.
- ≥ 4.0 hours to ≤ 6.0 hours.
- ≥ 8.0 hours to ≤ 10.0 hours, for patients 18 years or older.

The nominal mid-point time of 0, 2.5, 4.5, 5, 6.5 and 9 hours will be used for summaries of plasma concentrations. Plasma concentrations and PK parameters will be summarized showing the number of non-missing values (n), arithmetic mean, standard deviation, coefficient of variation (%), median, minimum and maximum. Where samples are reported as BLQ, a value of zero will be used in the summaries. Summary statistics will be presented to 3 significant figures.

Where data allow, the PK parameter AUC_{0-t} , will be derived at each visit by the PK vendor. A dose-normalized AUC_{0-t} will be calculated as AUC_{0-t} divided by the randomized dose per administration (12.5 or 25 mg/kg). This will include Visit 3, for consistency, where the first dose of IMP will be 2.5 mg/kg.

Plasma concentrations of CBD and its major metabolites 7-hydroxy-CBD (7-OH-CBD) and 7-carboxy-CBD (7-COOH-CBD) will be summarized by nominal mid-point time, visit and GWP42003-P arm. In addition, a dot plot of plasma concentrations for each patient, by nominal mid-point time will be created for each visit and GWP42003-P arm. The arithmetic mean will be highlighted on the plot. Additionally, a line plot of the arithmetic mean plasma concentration will be created with standard error bars by nominal mid-point time for each visit and GWP42003-P arm. These plots will be presented both a linear and semi-logarithmic scale for plasma concentration.

AUC_{0-t} and dose normalized AUC_{0-t} , for CBD and its major metabolites 7-OH-CBD and 7-COOH-CBD, will be summarized by visit and GWP42003-P arm. In addition, the ratio of 7-OH-CBD AUC_{0-t} to CBD AUC_{0-t} and the ratio of 7-COOH-CBD AUC_{0-t} to CBD AUC_{0-t} will be summarized. Box plots of AUC_{0-t} will be produced comparing visit on the x-axis, by parent and metabolite, and GWP42003-P arm. This will be repeated with parent and metabolite on the x-axis, by visit and GWP42003-P arm. Summaries and plots of AUC_{0-t} will be repeated by stratified age group.

Plasma concentration and AUC_{0-t} summaries may exclude individual time-points or visits for patients deemed to meet certain criteria that could affect exposure. These criteria include:

- Patients vomiting on or 1 day prior to the PK visit.
- Missed doses prior to the PK visit.
- IMP dose reduction.
- Cases of severe diarrhoea.
- Use of disallowed concomitant medication.

All exclusion will be detailed in a separate document finalized prior to unblinding. All data will be listed with data excluded from summaries flagged along with the reason for exclusion.

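### The single mean concentration–time line per visit and arm joins nominal times sampled in different patients, so its shape partly reflects who was sampled as well as kinetics

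*SAP*

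**What the plan says.** SAP Section 5.7.2 gives two schedules. The first is introduced by "For patients recruited under Protocol Version 2, PK samples were taken at the following time-points": pre-dose, "≥ 4.0 hours to ≤ 5.0 hours" and "≥ 6.0 hours to ≤ 7.0 hours". The second is introduced by "Patients recruited under Protocol Version 3 onwards, PK samples were taken at the following time-points": pre-dose, "≥ 2.0 hours to ≤ 3.0 hours" and a window from 4 to 6 h. Both end with a window from 8 to 10 h that is restricted by age: "hours, for patients 18 years or older".

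The schedules are then put on one time axis: "The nominal mid-point time of 0, 2.5, 4.5, 5, 6.5 and 9 hours will be used for summaries of plasma concentrations". For each visit and active arm, "a line plot of the arithmetic mean plasma concentration will be created with standard error bars by nominal mid-point time". The summary table and the individual dot plots use the same six nominal times, again by visit and arm only.

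The figure list in Appendix 6 (Table 21) shows the mean line plots by analyte, visit and scale, with no panel by protocol version or age. Section 5.7.2 does repeat summaries and plots by stratified age group, but only for AUC.

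**The concern.** A line through means invites the reader to see one group of patients followed over time. Here the patients change from point to point. If concentrations differ between the two protocol cohorts, or between adults and children, that difference appears on the plot as a rise, a dip or a faster or slower decline.

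The time bins add to this. The Version 2 window of 4 to 5 h lies wholly inside the later window of 4 to 6 h. Two samples drawn at the same time after dosing can therefore be plotted half an hour apart solely because of the protocol version.

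At stake is the reading of the mean profiles of CBD and its two metabolites after single and multiple doses, which serve an exploratory objective in Section 2.3.

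**Working it through.** **Step 1. Reproduce the nominal times.** Mid-point = (lower + upper)/2 for each window in Section 5.7.2.

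- Version 2: (4+5)/2 = 4.5; (6+7)/2 = 6.5; (8+10)/2 = 9.
- Version 3 onwards: (2+3)/2 = 2.5; (4+6)/2 = 5; (8+10)/2 = 9.

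With the pre-dose sample at 0, this gives 0, 2.5, 4.5, 5, 6.5 and 9 h, exactly the SAP's list.

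**Step 2. Who contributes at each time.**

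| Nominal time | Version 2, <18 | Version 2, ≥18 | Version 3+, <18 | Version 3+, ≥18 |
|---|---|---|---|---|
| 0 h | yes | yes | yes | yes |
| 2.5 h | – | – | yes | yes |
| 4.5 h | yes | yes | – | – |
| 5 h | – | – | yes | yes |
| 6.5 h | yes | yes | – | – |
| 9 h | – | yes | – | yes |

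**Step 3. Patients shared by the two ends of each segment.**

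- 0 to 2.5 h: Version 3 onwards only.
- 2.5 to 4.5 h: none.
- 4.5 to 5 h: none.
- 5 to 6.5 h: none.
- 6.5 to 9 h: Version 2 adults only.

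**Step 4. Illustrative size.** The SAP gives no version mix, adult share or concentrations, so every input in this step is an assumption. Let p be the adult share of those sampled, r the adult/child concentration ratio, and R the true ratio between two times, the same in every patient. With no difference between versions, when the earlier mean includes children and the 9 h mean does not:

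plotted ratio = R × r / (p × r + 1 − p)

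*9 h against 5 h, with R = 0.60 and p = 0.25:*

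- r = 0.8: 0.60 × 0.8 / (0.20 + 0.75) = 0.48/0.95 = 0.51.
- r = 1.25: 0.60 × 1.25 / (0.3125 + 0.75) = 0.75/1.0625 = 0.71.
- r = 1: 0.60, no distortion.

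*9 h against 6.5 h, over p = 0.2 to 0.4 and r = 0.7 to 1.3 (extremes at p = 0.2):*

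- No true change (R = 1): 0.7/0.94 = 0.74 to 1.3/1.06 = 1.23, so the plot moves by −26% to +23%.
- True fall of 30% (R = 0.70): 0.70 × 0.74 = 0.52 to 0.70 × 1.23 = 0.86, so the plot shows a fall of 48% to 14%.

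*Difference between versions.* If Version 2 concentrations were 0.8 or 1.25 times later ones, a truly flat profile would plot at 2.5, 4.5, 5 and 6.5 h as 1, 0.8, 1, 0.8 or as 1, 1.25, 1, 1.25. That zigzag comes from the order of the nominal times alone.

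**The case against.** The strongest defence has four parts.

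- **The plan does what the endpoint says.** Section 3.3.3 defines the endpoint as concentrations summarized by time window, and one nominal time per window does that. This stands for the table, where each row is a separate summary. It does not justify joining the rows with a line.
- **Other outputs show the same data.** Dot plots of each patient's values, a table with n, and listings are also planned. A reader might infer that the line plot is the only display of the time course; it is not. But the table and dot plots use the same pooled times, and the dot plot highlights the same means. A changing n shows that the denominator moved, not which group contributed.
- **Nothing in the SAP shows that concentrations differ by version or age.** This is correct. A reader might infer that the shape is produced by sampling alone, and the SAP does not support that: the line mixes true kinetics with composition. Repeating AUC by age group shows that age was considered for exposure, but that repeat does not reach the concentrations.
- **The plot carries standard error bars.** A reader might take an erratic 4.5 to 5 h step as evidence of bias. It need not be. With, say, 8 Version 2 and 30 later patients and a between-patient CV of 70% (all assumed), the standard error of the log ratio is about √(0.49/8 + 0.49/30) = 0.28 even if both groups share one curve. That is ordinary sampling error, which the bars partly show, and it is not counted here. The bars do not show or correct a systematic difference between groups.

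**Conclusion.** The point holds as a specific defect in a planned display. Which patients contribute at each nominal time follows exactly from Section 5.7.2 and needs no assumption. Followed as written, three of five segments join patients with no overlap, and the last step removes everyone under 18. Shape and decline then partly reflect who was sampled.

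The size cannot be fixed from the document. It is zero if the groups have equal concentrations. Under the assumed adult share of 25% and adult/child ratio of 0.8 or 1.25, a true 9 h/5 h ratio of 0.60 appears as about 0.51 or 0.71. The importance is low: this is descriptive output for an exploratory endpoint, the derivation of AUC is not in question, and no efficacy test depends on it.

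**What to change.** In Section 5.7.2 and the figure list, draw the mean lines and summarize concentrations separately by sampling schedule and by age. Each line then rests on one set of scheduled patients:

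- Version 2, under 18: 0, 4.5, 6.5 h.
- Version 2, 18 or older: 0, 4.5, 6.5, 9 h.
- Version 3 onwards, under 18: 0, 2.5, 5 h.
- Version 3 onwards, 18 or older: 0, 2.5, 5, 9 h.

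Print n at each time, since missing or excluded samples can still change the contributors within a line. If a pooled plot is kept, show the means unjoined and label the contributing group at each time.

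Merging the 4.5 and 5 h points into one is not a substitute. The merged mean would combine both cohorts, and no neighbouring post-dose time would have the same patients.

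The cost is SAP wording, extra panels or lines, and a smaller n with wider error bars per line. No new data are needed.
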